4.2 Recruitment

Participants will be identified through GP practices (Participant Identification Centres - PICs) within the Lindus Health Primary Care Network, and via social media campaigns to facilitate

recruitment. GP practices will be provided with a search for their registers to identify potential participants, who will be invited to take part in the trial via a text message directing them to the trial webpage where they will be able to download a Participant Information Sheet (PIS).

4.3 Baseline Measurements

Participants will attend a central clinic, where the following baseline measurements will be assessed by a qualified nurse:

- 1. Blood samples for the following biomarkers:
 - HbA1c
 - Insulin
 - Cholesterol ([total, LDL, HDL] and triglycerides)
 - Inflammatory markers (IL-6, IL-8, IL-10, CRP, TNF-a)
- Insulin Sensitivity Index Oral Glucose Tolerance Test for Insulin Sensitivity (ISI OGTT)
 - Participants will be asked to fast overnight and after a 10 to 12-hr overnight fast, they will administer a 75-g OGTT. Blood samples will be taken at the following timepoints 0, 30, 60, 90, and 120 min for the measurement of plasma glucose and insulin concentrations.
- 3. Blood pressure (systolic and diastolic)

Following analysis of the blood samples, only participants with a baseline HbA1c result within the range 5.8% - 6.5% will be considered eligible and subsequently randomised. HbA1c is the average blood glucose level for the last two to three months and so it will naturally vary. Consequently, the range for accepted baseline HbA1c results is slightly broader at baseline, than the initial inclusion criteria.

4.4 Withdrawal

Participants may choose to stop the intervention but may remain on study follow-up. If the participant withdraws completely, all recorded data will be analysed. If the participant starts antidiabetic medications during the trial, they will be withdrawn from the trial as antidiabetic treatment is an exclusion criteria. They will continue to receive follow up surveys to ensure safety monitoring. In addition, the Investigator may discontinue the participation of a participant from the study at any time, if this is considered necessary for any reason including, but not limited to:

- Ineligibility
- Clinical decision for other reasons

The type of withdrawal and reason for withdrawal will be recorded.

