1.0 Introduction

1.1 Study synopsis

Trial	Parallel randomised controlled trial
Phase	Proof-of-concept
Sample size	60
Study population	Otherwise healthy men and postmenopausal women aged 18-70 with signs of prediabetes, but not clinically diagnosed with diabetes.
Duration	24 weeks
Background	Pre-diabetes is characterised by high blood glucose levels, high plasma cholesterol, low-density lipoprotein (LDL) and high-density lipoprotein (HDL). Dietary fibre consumption has been hypothesised to improve these metabolic parameters through microbial fermentation and the subsequent production of short-chain fatty acids (SCFAs).
Objectives and aims	This trial will investigate whether a powdered fibre mix (myota Metabolic Regulator) helps maintain healthy blood glucose levels in participants with prediabetes, where high blood sugar is a risk of diabetes.
Recruitment strategy	Participants will be identified through the Lindus Health Primary Care Network, and social media advertising may also be used. Participants will complete online pre-screening, trial registration and informed consent. Eligibility will be confirmed by the Research Nurse during a video call with the participant.
Randomisation	Participants will be randomised to Placebo or the Myota Metabolic Regulator (powdered fibre mix) with a 1:1 randomisation ratio stratified by gender and BMI.
Intervention	The functional food, Myota Metabolic Regulator, consisting of 20g of a powdered fibre mix, to be taken daily alongside usual diet for 24 weeks.
Comparator Group	Placebo will be 2g of powdered cellulose, to be taken daily alongside usual diet for 24 weeks.
	Participants will be asked to attend an appointment (~2.5-3 hours) at a central clinic in London at baseline, week 16 and week 24. During the appointment, a nurse will obtain blood samples for biomarker measurements (see Outcomes for full list), ask the participant to complete an OGTT (baseline and week 16 only) and collect blood pressure recordings. In addition, participant surveys will collect any (Serious) Adverse Events at the end of weeks 4 and 8 and then monthly, usability testing at 16 and 24 weeks, and intervention adherence on a daily basis for 24 weeks. The Lindus Health Research Nurse will contact participants throughout the trial.

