2.0 Study Methods

2.1 Trial design

This trial is a two-arm, individually randomized, single-blind placebo-controlled trial. The total trial duration is 24 weeks. Participants will be assigned to the intervention or placebo for 24 weeks. Primary and secondary outcomes will be assessed at baseline, 16, and 24 weeks (*Section 1.3*).

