3.3 Analysis populations

3.3.1 Intention to Treat (ITT)

All randomised study participants. This will be seen as the primary population for the analysis.

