4.1.2 Exclusion Criteria

- Receiving medication to treat Type 1 or Type 2 diabetes in the previous 6 months
- Have a Body Mass Index (BMI) <25 kg/m² and >45 kg/m²
- Loss of more than 5% body weight in last 3 months
- Current participation in weight loss program or planned in the next 16 weeks
- Steroid use (except for over the counter NSAID's, topical steroids and inhalers)
- Severe hepatic diseases (including chronic persistent hepatitis, liver cirrhosis or the co-occurrence of positive hepatitis B virus surface antigen and abnormal hepatic transaminase (serum concentrations of alanine transaminase or aspartate transaminase >2.5× the upper normal limit))
- Continuous antibiotic use for >3 days within 4 weeks prior to enrolment
- Continuous use of weight-loss drug for within 3 months of study entry
- Gastrointestinal surgery (except for appendicitis or hernia surgery or co-existing pathology (Crohn's disease, celiac, endometriosis, prostate cancer))
- Severe mental illness within 6 months prior to enrolment
- Receiving drug therapy to treat cholecystitis, peptic ulcers, urinary tract infection, acute pyelonephritis, urocystitis or hyperthyreosis
- Pituitary dysfunction
- Severe organic diseases, including cancer, coronary heart disease, myocardial infarction or cerebral apoplexy
- Infectious diseases, including pulmonary tuberculosis and AIDS
- History of alcoholism or substance abuse
- Significant dyslipidaemia (>3 month use of low dose statins permitted*)
- Severe hypertension (>160/100)
- Using any food supplements for blood glucose control (e.g. chromium picolinate) within 2 months of trial entry

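### The per-protocol analysis, the plan's only missing-data check, never varies the imputed values; this matters most for participants who start antidiabetic medication before week 16

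*SAP*

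**What the plan says.** **Medication starters.** SAP section 4.4 states: "If the participant starts antidiabetic medications during the trial, they will be withdrawn from the trial as antidiabetic treatment is an exclusion criteria". The next sentence gives the only follow-up named for them: "They will continue to receive follow up surveys to ensure safety monitoring". The same section treats those who merely stop the product differently: "Participants may choose to stop the intervention but may remain on study follow-up". It also says that data already recorded from complete withdrawals are analysed, and that "The type of withdrawal and reason for withdrawal will be recorded". The criterion relied on, in 4.1.2, is worded as a look-back at entry: "Receiving medication to treat Type 1 or Type 2 diabetes in the previous 6 months".

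**Measurement.** HbA1c comes from blood drawn by a nurse "at a central clinic in London at baseline, week 16 and week 24" (section 1.1). Section 2.1 agrees: "Primary and secondary outcomes will be assessed at baseline, 16, and 24 weeks". No trial HbA1c falls between baseline and week 16. The primary outcome is the percent change over that interval (5.1.1).

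**Analysis.** The ITT set is "All randomised study participants. This will be seen as the primary population for the analysis" (3.3.1). Section 5.3 specifies multiple imputation and cites reference 11. It gives no missingness assumption and no rule for values after medication start. The title of reference 11 concerns protocol deviation but does not say which assumption is adopted. Sections 3.3.2 and 5.5 give PP the job of showing whether conclusions depend on missing-data assumptions. PP requires completion of the trial without significant deviation, and section 3.2 counts taking the product on fewer than 70% of days as such a deviation.

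**The concern.** A missing-data sensitivity analysis should hold the population fixed and vary what is assumed about the unseen values. PP does the reverse: it removes people with unseen values and assumes nothing about them. It also removes people with observed outcomes but low adherence, so a difference between PP and ITT cannot be attributed to missingness.

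Medication starters are where this bites. Starting glucose-lowering treatment in a prediabetes trial with an HbA1c endpoint is plausibly related to the outcome. With no HbA1c between baseline and week 16, a missing-at-random model has no on-study HbA1c from which to learn of a deterioration. Recorded withdrawal reasons would show how many started in each arm. No planned analysis would show what they do to the estimate, and a blood sample not taken cannot be recovered.

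**Working it through.** **1. The plan's own figure.** Section 2.3 gives 30 per arm, 80% power and d = 0.74. A two-sided t-test at 0.05 (noncentral t) has 80.5% power at d = 0.74, and the effect detectable with 80% power is d = 0.736. The figure reproduces and is not disputed. The SE of the difference is sqrt(2/30) = 0.258 SD.

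**2. Who is affected.** A start before week 16 appears to cost the primary value. A start between weeks 16 and 24 leaves the recorded week-16 value in the ITT analysis, but the participant leaves PP as a non-completer.

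**3. Size if the target is HbA1c without the drug's effect.** The SAP gives no rates, so these inputs are assumptions: k = excess starters before week 16 in one arm; g = 0.5 to 1.5 SD, the amount by which their change would exceed the missing-at-random imputed value. Shift = (k/30) × g. The power column puts the excess on placebo with d = 0.736. The type I column puts it on active with no true effect. The SE is unchanged.

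| k | Shift (SD) | % of d = 0.736 | Shift in SE | Power | Type I error |
|---|---|---|---|---|---|
| 1 | 0.017–0.050 | 2.3–6.8 | 0.06–0.19 | 78.2–74.3% | 5.05–5.4% |
| 2 | 0.033–0.100 | 4.5–13.6 | 0.13–0.39 | 76.3–67.8% | 5.2–6.7% |
| 3 | 0.050–0.150 | 6.8–20.4 | 0.19–0.58 | 74.3–60.7% | 5.4–8.8% |

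With g = 2 the shift is 1/30 × 2 = 0.067 for k = 1 and 3/30 × 2 = 0.20 for k = 3. With equal numbers and equal g in both arms it is zero.

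**4. Size if the target is HbA1c as observed on the drug.** Let m be the drug's effect in SD (assumed). Shift = (k/30) × (g − m). For k = 3 and g = 1: m = 0 gives 3/30 × 1 = +0.10; m = 1 gives 0; m = 2 gives 3/30 × (−1) = −0.10. The bias can vanish or reverse.

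**5. What PP adds.** Simulated trials with 30 per arm, starters on placebo only, g = 1 and 20 imputations (4,000 trials):

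| k | Full data | Missing-at-random imputation | Completers only |
|---|---|---|---|
| 1 | 0.765 | 0.732 | 0.732 |
| 3 | 0.838 | 0.740 | 0.740 |

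The completers-only result, which stands in for PP, repeats the imputed one. Adding a delta of 1.0 SD to the starters' imputed values at k = 3 gives 0.840 against 0.841 for full data in that run. The recovery is close because the delta matches the assumed g.

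**6. Same starting rule in both arms.**
- *Trigger = true change plus noise of equal variance, true effect 0.736.* When 3.3%, 6.7% or 10% of placebo start, 0.9%, 2.2% or 3.6% of active start. The estimate moves toward zero by 0.037, 0.061 or 0.080 SD (5%, 8% or 11% of d).
- *Harsher rule: starters are those whose outcome lies beyond 1.28 to 2.0 SD above the placebo mean, with 70–100% of them lost; completers only stands in for imputation.* About 0.5 to 3.0 placebo and 0.1 to 0.7 active participants are lost. A true 0.74 falls to between 0.60 and 0.71, with power of 69% to 80%.
- With no true effect, neither rule shifts the estimate, and rejection under the harsher rule stays near 5%.

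**The case against.** **The lost sample is inferred.** A reader might conclude that the SAP forbids week-16 blood after medication start. It does not: 4.4 neither stops nor schedules sampling for starters, and the protocol is not shown. This stands, so the point on 4.4 is limited to what appears to happen.

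**PP is not always uninformative.** A reader might infer that PP can never reveal dependence on the imputation. That is too strong. If the imputation were not missing-at-random, ITT and PP could differ; in step 5, the delta-adjusted 0.840 against 0.740 for completers would show it. Section 5.3 names no assumption, so either case is possible. What remains is that PP cannot vary imputed values within the full randomised set and also selects on adherence.

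**A placebo excess is not simply conservative.** That direction holds only for HbA1c without the drug's effect, a target the SAP does not state. A week-16 sample taken on the drug would not observe that quantity.

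**Sections 3.3.1, 4.4 and 5.3 do not conflict.** Withdrawn participants stay in the ITT set and are imputed. Applying an entry exclusion during follow-up is a design choice, and the look-back wording in 4.1.2 does not make it an error.

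**Starts may be rare.** Baseline HbA1c must be 5.8–6.5%, and an early start would depend on testing outside the trial. In a 60-person proof-of-concept trial there may be few starters or none. This limits the expected size. The PP weakness applies to any missing outcome and does not depend on it.

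**Conclusion.** The point holds in a bounded form. The firm part is that the analysis named as the missing-data check does not vary missing-data assumptions in the randomised set and confounds missingness with adherence. The less certain part is that week-16 HbA1c appears to be lost for those who start medication before that visit, a loss plausibly related to the outcome.

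The effect is small for a single excess starter: at most about 0.05 SD, or 0.19 SE, for g up to 1.5. It is material only from about two or three: up to 0.10 and 0.15 SD. These figures rest on assumed k and g, missing-at-random imputation and a without-medication target. Another target or imputation assumption would change the size and possibly the sign. The documents do not support saying that the primary result will be biased. This is an improvement the plan should make, held with medium confidence.

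**What to change.** 1. **Section 5.5.** Keep PP as an adherence analysis. As the missing-data check, add a delta-adjusted multiple-imputation analysis of the primary outcome in all randomised participants. Use deltas in both directions and allow them to differ by arm, for example −1.5 to +1.5 SD of change in steps of 0.5. Report medication starters by arm beside it.
2. **Section 4.4.** Separate withdrawal from the product from withdrawal from data collection. Suggested wording: *Consenting participants who start antidiabetic medication continue to give the scheduled week-16 and week-24 blood samples; the drug and its start date are recorded.* If the protocol already provides this, say so here.
3. **Section 5.3.** Before the 16-week interim analysis (2.4), state whether values after medication start are used as observed or replaced by imputation, and report the other as supplementary.

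The cost is wording in three sections, one extra sensitivity analysis and slightly more follow-up at visits already scheduled. Protocol and consent text, not shown, may need aligning. One downside remains: observed values include the drug's effect, so they do not answer a without-medication question. No view is taken on treatment or on whether these participants stop the product.

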5.5 Analysis

5.1 Outcome definitions

5.1.1 Primary Outcome

• HbA1c (%). The percent change between baseline and 16 weeks will be used for analysis.

5.1.2 Secondary Outcomes

- HbA1c (%) between baseline, 16 and 24 weeks
- Glucose (mmol/L) between baseline, 16 and 24 weeks
- Insulin (µU/mI) between baseline, 16 and 24 weeks
- Insulin sensitivity (µU/ml) from ISI-OGTT between baseline and 16 weeks
- Total cholesterol (mmol/L) between baseline, 16 and 24 weeks
- LDL (mmol/L) between baseline, 16 and 24 weeks
- HDL (mmol/L) between baseline, 16 and 24 weeks
- Triglycerides (mmol/L) between baseline, 16 and 24 weeks
- IL-6 (ng/L) between baseline, 16 and 24 weeks
- IL-8 (ng/L) between baseline, 16 and 24 weeks
- IL-10 (ng/L) between baseline, 16 and 24 weeks
- CRP (ng/L) between baseline, 16 and 24 weeks
- TNF-a (ng/L) between baseline, 16 and 24 weeks
- Diastolic blood pressure (mm/Hg) between baseline, 16 and 24 weeks
- Systolic blood pressure (mm/Hg) between baseline, 16 and 24 weeks

5.2 Analysis methods

5.2.1 Descriptive Statistics

All outcome measures will be presented using descriptive statistics. Continuous variables will be summarised using minimum, maximum, mean, standard deviation (SD), median, and interquartile range (IQR). Additionally, the distribution of each variable will be presented using violin and box-plots or other appropriate graphical formats. Binary and categorical variables will be presented using percentages and counts. Descriptive statistics will be presented for each outcome variable at each time point.

For (S)AE, the absolute and relative frequency of each (S)AE will be reported over the whole study duration (24 weeks).

5.2.2 Primary Outcome

A two-tailed t-test will be used to compare the percent change in HbA1c levels from baseline to 16 weeks between treatment and placebo.

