2.2 Randomisation

Consenting participants who have met all of the eligibility criteria and completed the baseline assessment will be individually randomised into one of the two groups, using a web based system (Sealed Envelope), at a ratio of 1:1, stratified by gender and BMI.

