2.3 Sample size

This study aims to recruit 60 participants, men and post-menopausal women aged 18-70 diagnosed with pre-diabetes, but not receiving treatment for type 2 diabetes. As this is a pilot study, our sample size has not been derived statistically, but informed based on previous studies assessing fibre-based interventions in pre-diabetes cohorts. Our sample size is therefore consistent with previous studies assessing fibre-based interventions in similar populations. Results from previous studies (Zhou et al. 2018, n = 43; Peterson et al., 2018, n = 68) suggest that 60 participants is an adequate sample size to capture meaningful differences in our primary and secondary outcome measures. A sample size of 30 in each arm results in a power of 80% to detect effects of at least d = 0.74.

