3.0 Statistical Principles

3.1 Confidence intervals and P values

Effects will be considered statistically significant if the associated *p*-value is smaller than 0.05.

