5.2.3 Secondary Outcomes

Two-way repeated measures ANCOVA with one within-subject factor (time) and one between-subject factor (condition) will be used to compare HbA1c levels, insulin levels, total cholesterol levels, LDL, HDL and triglyceride levels, inflammatory biomarker levels (including IL-6, IL-8, IL-10, CRP and TNF-a), and diastolic and systolic blood pressure. Post-hoc one-tailed paired t-tests will be performed on significant main or interaction effects to compare differences between groups over time. For non-normally distributed outcome variables, robust ANCOVA and post-hoc comparisons with trimmed means are used. In addition, a two-tailed t-test will be used to compare the change in insulin sensitivity from baseline to 16 weeks between treatment and placebo.

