5.4 Additional analyses

Exploratory analyses will examine interdependencies of the primary and secondary outcomes, and sub-group analyses including the effects of baseline HbA1c, insulin sensitivity, fasting glucose, sex and age groups on the percent change in HbA1c level.

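### The primary t-test on percent change in HbA1c ignores baseline HbA1c and the stratification factors; adjusting would cost about 1 point of power and, under assumed slopes, could gain up to about 8

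*SAP*

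**What the plan says.** Section 5.1.1 defines the primary outcome: "The percent change between baseline and 16 weeks will be used for analysis". Section 5.2.2 gives the whole primary analysis: "A two-tailed t-test will be used to compare the percent change in HbA1c levels from baseline to 16 weeks between treatment and placebo". Significance is declared when the p-value "is smaller than 0.05" (section 3.1), and section 2.3 states: "A sample size of 30 in each arm results in a power of 80% to detect effects of at least d = 0.74".

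Participants are randomised "at a ratio of 1:1, stratified by gender and BMI" (section 2.2). Sections 4.1.1 and 4.3 require a baseline HbA1c of 5.8% to 6.5% before randomisation, so all three covariates are known by then.

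No other section supplies an adjusted primary comparison:

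- The repeated measures ANCOVA in section 5.2.3 is secondary and names only time and condition.
- Section 5.3 deals with imputation.
- Section 5.4 lists, as exploratory subgroup work, "the effects of baseline HbA1c, insulin sensitivity, fasting glucose, sex and age groups on the percent change in HbA1c level".
- The sensitivity analysis (section 5.5) changes only the population.

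Section 5.2.3 treats one secondary outcome in the same unadjusted way: "a two-tailed t-test will be used to compare the change in insulin sensitivity from baseline to 16 weeks between treatment and placebo".

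**The concern.** Dividing by baseline is not the same as adjusting for it. Percent change is free of baseline only if week-16 HbA1c is proportional to baseline. Section 4.3 says of HbA1c that "HbA1c is the average blood glucose level for the last two to three months and so it will naturally vary". Within-person variation of that kind makes a slope of week-16 on baseline below 1 plausible. If the slope is below 1, participants with a high baseline tend to fall and those with a low baseline tend to rise. A chance difference between the arms at baseline then carries into the estimated treatment effect.

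The stratification factors raise a second issue. If gender or BMI predicts percent change, stratification has already balanced it, but the plain t-test still counts its variation as noise. The test is then conservative.

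What is at stake is precision in a trial that reaches 80% power only for a large effect, and protection of its one primary estimate against chance imbalance. An overall excess of false positives is not at issue.

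**Working it through.** **1. The plan's own figure.** Inputs: 30 per arm and d = 0.74 (section 2.3), two-sided alpha 0.05 (sections 3.1 and 5.2.2). With noncentrality d·√(30/2) and 58 degrees of freedom, power is 80.5% at d = 0.74 and exactly 80.0% at d = 0.7356. The stated figure reproduces.

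**2. Cost when the covariates predict nothing.** The adjusted model has an intercept, arm, baseline HbA1c, gender and BMI (taken as two levels), so residual df = 60 − 5 = 55. Losing degrees of freedom alone takes power at d = 0.7356 from 80.0% to 79.9%. Allowing also for chance imbalance in baseline HbA1c, the one covariate that is not stratified, the loss is 0.8 point.

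**3. Gain when they do predict.** If the covariates explain a share R² of the outcome variance, the effective effect size becomes d/√(1 − R²). From a starting power of 80.5% at d = 0.74, with imbalance in baseline HbA1c allowed for:

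| R² | Change in power (points) |
|---|---|
| 0 | −0.8 |
| 0.05 | +1.2 |
| 0.10 | +3.2 |
| 0.15 | +5.2 |
| 0.20 | +7.2 |
| 0.25 | +9.2 |
| 0.30 | +11.1 |

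**4. What R² might be.** The SAP gives no SD, slope or correlation. Assume a baseline SD of 0.17 within the 5.8% to 6.5% window, slope b, and residual SD s. Percent change is close to a constant multiple of the absolute change, so the share explained by baseline is approximately R² = (1 − b)²·0.17² / [(1 − b)²·0.17² + s²]. For b = 0.5 and s = 0.20, this is 0.007225/0.047225 = 0.15.

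The scenarios were simulated with 32,000 trials each, blocks of 4 within gender by BMI, and the effect set at d = 0.7356:

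| Slope | Residual SD | R² from baseline | t-test power | Adjusted power |
|---|---|---|---|---|
| 0.5 | 0.15 | 0.24 | 80.7% | 89.0% |
| 0.5 | 0.20 | 0.15 | 80.2% | 85.3% |
| 0.7 | 0.20 | 0.06 | 80.2% | 81.7% |
| 0.9 | 0.20 | 0.01 | 80.2% | 79.5% |
| 1.0 | 0.20 | 0 | 80.5% | 79.5% |

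**5. Prognostic strata.** If gender and BMI each shift the outcome by half a residual SD (residual SD 0.20), power is 82.1% against 89.0% at slope 0.5, 81.8% against 85.8% at slope 0.7, and 81.4% against 84.0% at slope 0.9. With no treatment effect, the t-test rejects in about 3.9% of trials and the adjusted model in 5.0%.

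**6. Effect of a chance baseline imbalance.** The standard error of the baseline difference is 0.17·√(2/30) = 0.044 HbA1c points, and a larger difference arises in about one trial in three. The unadjusted estimate then shifts by (1 − b)·0.044. With residual SD 0.20:

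| Slope | Shift (points) | Effect at d = 0.7356 (points) | Shift as share of effect |
|---|---|---|---|
| 0.5 | 0.022 | 0.160 | 14% |
| 0.7 | 0.013 | 0.152 | 9% |
| 0.9 | 0.004 | 0.148 | 3% |

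The effect column is 0.7356·√[(1 − b)²·0.17² + 0.20²].

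At an imbalance near 1 standard error, null rejection is 4.6% to 5.6% for both tests. Near 2 standard errors (exceeded in under 5% of trials), the t-test rejects a true null in 14.0% (slope 0.5, SD 0.15), 8.5% (0.5, 0.20) or 7.1% (0.7, 0.20) of trials, against 5.0%, 5.7% and 5.2% for the adjusted model.

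**7. Insulin sensitivity.** Baseline is not range-restricted here. With equal SDs at both visits and an assumed correlation r, R² = (1 − r)/2. Simulated power, t-test against adjusted, is 80% against 89%, 85%, 83% and 81% at r = 0.5, 0.7, 0.8 and 0.9.

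**The case against.** The strongest reply is that nothing here is an error. The t-test is fully specified, two-sided, applied to the defined outcome and consistent with the power statement. The trial is a proof-of-concept study whose sample size was not derived statistically, so a few points of power matter less than in a confirmatory trial. That stands: this is an improvement in precision and does not correct an invalid test.

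The size of the gain is also assumed. The 8 points come from the most favourable scenario. At slope 0.7, with strata that do not predict outcome, the gain is about 1.5 points, and at 0.9 or 1.0 there is a small loss. The remark in section 4.3 explains why the baseline window is widened; it makes a slope below 1 plausible but does not favour 0.5 over 0.9. A separate set of assumptions (SD 0.2 to 0.3 before truncation, correlation 0.5 to 0.9) has baseline alone explaining about 2% to 18% of the variance, which places 8 points at the optimistic end for baseline alone. Nor is 8 a ceiling, since R² of 0.30 would give about 11. The cost of about 1 point relies on stratification balancing gender and BMI; if all three covariates could be imbalanced, it would be about 2 points. All of this stands as a limit on the figures.

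Finally, the 14% null rejection applies only to rare imbalances in the most favourable scenario. Over all randomisations, the t-test rejected a true null in about 5% of trials when strata were not prognostic. That also stands, and the recommendation does not rest on the 14%.

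None of this answers the omission. The covariates are in hand, the design stratifies on two of them, and no section uses any of them in the primary comparison.

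**Conclusion.** The point holds. The planned test is valid, and conservative if gender or BMI is prognostic, but it does not match the stratified design and leaves out a baseline value that every randomised participant has. Adjustment costs about 1 point of power if no covariate predicts percent change, taking two BMI levels and strata balanced by design. Under the assumed slopes and residual SDs it gains between nothing and about 8 points. That 8 is the top of an assumed range and not a bound that the SAP provides. Adjustment also removes a shift of roughly 3% to 14% of the detectable effect when the arms differ by one standard error at baseline. The omission is certain; the size of the gain is not. With a small, nearly fixed downside, the change is worth making.

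**What to change.** Replace the text of section 5.2.2 with wording such as:

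> In the ITT population, the arms will be compared on week-16 percent change in HbA1c with a linear model (ANCOVA) containing arm, baseline HbA1c as a continuous covariate, gender, and BMI stratum as used in randomisation. The model will be fitted in each imputed data set and the results pooled by Rubin's rules. The adjusted mean difference, its 95% confidence interval and the two-sided p-value will be reported. The unadjusted t-test will be reported as supportive.

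In section 5.2.3, analyse change in insulin sensitivity with the same model, with baseline insulin sensitivity in place of baseline HbA1c.

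The endpoint, population, imputation and sample size stay as they are, and no new data are needed. The cost is SAP wording, three residual degrees of freedom (58 to 55 with two BMI levels), and about 1 point of power if the covariates turn out to be uninformative.
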